5.4 Study Enrollment Procedures

5.4.1 Recruitment

Clinical Practices of Investigators

Infertile couples presenting for consultation with an obese female and unexplained infertility (after clinical confirmation of their eligibility for admission into the study based on inclusion and exclusion criteria) will be approached to participate by the research coordinator or non-care providing physician. In the recruitment visit, study details including the expectations of lifestyle modification, as well as the experimental nature of the preconception intervention will be explained. Risks and benefits will be thoroughly discussed and consents given to the patient and partner.

Hospital/Local Health Care Referrals

Subjects will be recruited at each site from individual practice(s) of the investigators as noted above as well as faculty/resident clinics. Ongoing contact with practice and faculty members as well as with residents will be made by the investigators and coordinators, reminding them of the inclusion criteria, importance of the study, etc. In addition, the investigators will describe the study to members of other departments in the hospital, primarily family practice, medical endocrinology, urology, and gynecology who also see and treat these patients. Contact with local physicians will be made and/or grand rounds will be given to disseminate information about the study.

Referrals from Study Participants

Study participants often refer friends, acquaintances and colleagues to be potential participants.

Local Publicity Office

Investigators will meet with their local Public Relations offices and plan a news release about the study. They will also make themselves available for any newspaper, radio, or TV stories that may increase public awareness of the study. The full gamut of local media sources should be utilized. Often there is greater yield with more extensive coverage in smaller local outlets as opposed to brief mentions in outlets with larger circulation. News releases will mention the uniqueness of the study.

Local Advertisements

Advertisements will be placed in local newspapers and will be continued on a regular basis if response is good.

Contact with infertility support groups

Contact will be made with both national and local support groups to spread information about the study through informational brochures and/or participation in local meetings. The American Infertility Association also may be helpful in promoting awareness of this study.

National Professional Organizations

Contact will be made with the publicity office of The American Society for Reproductive Medicine, and other potentially helpful organizations to solicit their support and potential informational releases.

Web sites

The study will be prominently displayed on the RMN web site. Additionally each RMN center should have a web page devoted to this study with general as well as contact information. Information should also be available at the NICHD web site with links to each RMN center. An ad should also be placed at "Center Watch" on the web.

National Advertising

We would consider placing a trial ad in the health section of a select or a series of selected national publications with all of our local numbers/contacts.

IRB Approval

It is expressly acknowledged that all informational material that could be construed to be advertising will be approved by the appropriate IRB prior to dissemination.

5.5 Procedures for Tracking Sources of Subjects and their Disposition

We will track all contacts from subjects interested in the study. We will develop a pre-screening list that documents date and point of contact, eligibility based on telephone screening, and follow-up if subject meets prescreening and is interested in further participation. The consent form is mailed or emailed prior to the screening visit which is the next point of contact.

5.6 Obtaining Informed Consent

Once potential couples have been prescreened, they will be referred to the site clinical coordinator or his/her designee for a screening visit. The consent will be explained to potential subjects and their partners by the coordinator or possibly the physician investigator depending on the clinical circumstances.

Inclusion and exclusion criteria will be reviewed. After the study has been completely explained to the potential couple, they will be given the informed consent documents to review (sample consent forms, in the format of Penn State University, are included in Section 10). Some individuals may wish to complete the informed consent process at the time of this discussion. In these cases the informed consent documents will be signed once all questions are resolved. In other cases the subjects may wish to take the consent forms home for further consideration. In these cases the coordinator will confirm the couple's willingness to be contacted, and set up a tentative timeframe to be back in touch with the subjects. The consents can be signed either with the coordinator or with a physician once all questions have been answered to the satisfaction of the potential patient and partner. A signed informed consent document, approved by the IRB at the study site, will be confirmed on all subjects prior to the baseline evaluation. The PI at each RMN site should not simultaneously be managing the care of a patient in the study and be the primary caregiver for a study participant, as specified in the NICHD clinical Research Policy guidelines.

In order to be eligible for enrollment and randomization, each member of the couple must be confirmed to meet all inclusion and exclusion criteria described above.

5.7 Intervention Group Assignment

After screening is completed the information will be uploaded to the WebEZ system electronically, and randomization will be performed by the program at the time of the randomization visit. Subjects will be immediately informed of their treatment assignment and orientation will begin.

6 Study Interventions

6.1 Interventions, Administration and Duration

Phase I – Preconception Treatment

Overview

Phase 1 will involve randomization to either an Intensive Lifestyle Modification program or a Standard Physical Activity Program. Each will last 16 weeks. The Intensive Lifestyle Modification Program will consist of an over the counter anti-obesity drug, orlistat, caloric restriction assisted by the use of meal replacements, and increased physical activity. The Standard Physical activity Program will consist of increased physical activity alone. All subjects will receive folic acid supplementation throughout all phases of the study.

Our goal in designing the lifestyle modification program is to develop simple methods that are easily comprehended by our subjects and study personnel. Therefore we are dispensing with labor intensive recall questionnaires of diet and activity that are frequently utilized in such studies but have little correlation with change in hard outcomes such as weight or biochemical parameters. We will create identical on-site in-person study visits and self-monitoring schedules for both lifestyle modification groups. We will utilize in both groups wireless devices that monitor activity (Fitbit) and weight (Fitbit Aria Scale) and automatically upload data to a central website (maintained by the DCC with appropriate consultants). This will enable both self-monitoring by the subject and central monitoring by the study personnel (who will provide devices, a web account, and joint access to the website). This will allow both subjects and study personnel the ability to view integrated and time related data and will also save time for subjects and study personnel. Finally, it allows a seamless record of weight and activity from preconception to conception to pregnancy to delivery. We will develop algorithms to address poor compliance with activity recommendations in both groups based on Fitbit self-monitoring as well as lack of weight loss within the intensive lifestyle modification with caloric restriction group. We will pilot text-based automated responses on smart phones to achieve these goals, as well as using more traditional (phone or email) methods for those without access to smart phones. Both groups will have similar formal site visit schedules and interactions with study personnel.

Intensive Lifestyle Modification: The primary focus of this modification will be to achieve weight loss as well as to increase physical activity. We will use a multifocal approach to achieve weight loss, utilizing meal replacements as well as a gastric lipase inhibitor (orlistat OTC - brand name Alli at 60 mg per dose) to prevent fat absorption. Multifocal approaches have been shown to increase weight loss beyond single therapy based interventions.

Medication (Orlistat) will be initiated at a dose of 60 mg per meal at lunch and dinner. We will skip the morning dose, as subjects have a low fat meal replacement (MR) breakfast: MRs as basis of a hypocaloric diet (~1200-1500 kcal/d). We, led by [name], will develop a complete daily diet plan for the 16 week intervention plan with meal replacements that includes two prepared entrees for lunch and dinner and a cereal bar or beverage. The meal replacements

will be provided without cost to the participants in this treatment group. In addition, subjects will be instructed to consume two servings of fruit, 3 servings of vegetables, and two servings of low fat dairy per day. This diet will provide about 1100 calories with this macronutrient profile: 30% calories from protein, 45% calories from carbohydrate; and 25% calories from fat. Since we want to provide 1200 calories per day, there are 100 calories that can be consumed as desired. This meal plan totals approximately 1200 kcal/d and is consistent with the lifestyle modification in the Look AHEAD study.⁷⁹ Participants will be provided full instructions on how to use MRs and will develop a daily schedule for consuming them. At the randomization visit in Phase I, participants will receive instructions on ordering MRs directly from the Nutrisystem web site which will be shipped directly to their house. They will receive a monthly code to order further meal replacements. They will also at the randomization visit receive a two month supply of medication. We will ask subjects to weigh themselves at home on a weekly basis and will capture results automatically with the Fitbit Aria scale.

Increased Physical Activity Subjects will be asked to use the Fitbit Physical Activity Monitor during the screening phase to establish a mean number of steps over a 7 day period. This will then form the baseline number of steps. This baseline average of steps will be used as the starting point for increasing average steps a day by 500 steps a day per week until the desired maximum of 10,000 steps is reached. Subjects will be asked to maintain that level of physical activity throughout the study.

6.1.1 Determine Baseline Physical Activity

Subjects will be dispensed a Fitbit Physical Activity monitor during the randomization visit which will be used to determine average daily steps over a week's time.

Standard Physical Activity Intervention: This will be identical to the physical activity described above for the intensive physical activity group. There will be no dietary recommendations, no use of meal replacements, and no use of anti-obesity drugs. Subjects will have the same monitoring schedule both on site and off site as subjects in the intensive lifestyle modification.

Conception during Lifestyle Modification We will encourage intercourse without barriers during the lifestyle modification phase and welcome any pregnancies which happen. They will be managed identically as though that occur during the empiric infertility treatment phase of this study (Phase II below). Of course such pregnancies will be analyzed by treatment group according to intention-to-treat (ITT) principles. We are using safe and widely utilized lifestyle modifications. We are using an OTC weight loss drug, Alli, that has no known early adverse pregnancy effects and we will immediately discontinue it if pregnancy occurs. The ability to conceive at all points in this study will increase the appeal to participate and also the external validity of our results. No one with infertility wants to stop attempting pregnancy as part of infertility treatment. This also led us to reject using the oral contraceptive pill as a control arm for unexplained infertility.

Phase II – Standardized infertility treatment

After completion of Phase I (or 16 weeks of pretreatment), all subjects will enter Phase II. This phase will be universally administered to all participants in an open label, but standardized fashion. In this part of the study, subjects will receive three cycles of ovarian stimulation/hCG

trigger for ovulation/ timed IUI and followed by midluteal visit. We will clamp weight and activity in both groups and continue to monitor with the Fitbit and the Aria scale. We will modify and streamline the study procedures from our AMIGOS study.

Phase III – Pregnancy

There will be no treatment intervention during pregnancy, though we will continue to monitor weight and have trimester study visits.

Phase IV – Pregnancy Registry

All subjects who deliver will be encouraged to participate in our Pregnancy Registry which currently provides infant follow up till age 3. This is currently a separate protocol and we will also obtain separate informed consent for participation in this protocol.

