4.1.1 Treatment Design

This will be a two-arm, multi-center, prospective randomized trial of two types of lifestyle modification in obese women with unexplained infertility who will be randomized to either an intensive lifestyle modification with weight loss and increased physical activity or a standard lifestyle modification consisting of increased physical activity for 16 weeks prior to initiating infertility treatment with an oral drug, clomiphene, to stimulate follicular development followed by intrauterine insemination (IUI). The lifestyle modifications will be open label with adequate allocation concealment and the randomization ratio will be equal between modifications (1:1).

The appropriate study candidates will be recruited from the main sites of the Reproductive Medicine Network and their ancillary partners. Recruited subjects will meet the inclusion and exclusion criteria detailed below. Monitoring of this trial at all sites will be conducted by the RMN Data Coordination Center, with progress reports provided to the RMN Data and Safety Monitoring Board (DSMB) no less than every three months in order to review trial progress and subject safety.

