7.2 Timing of Evaluations

Screening visit(s):

Although we anticipate that the items described below could be completed in a single visit, we will allow coordinators to divide them into two visits. For example, if the subject or couple has had little to no prior evaluation, it may be time and cost effective to obtain parameters in a stepwise fashion. We anticipate that consent, biometrics, and medical history would be obtained at first visit, whereas we would distribute kits to collect saliva, stool and dispense the FitBit activity monitor at the second visit for subjects with a high probability of randomization.

1. Obtain informed, signed consent from female and male partner.

Female and partner must specifically be made aware of potential drug complications and adverse outcomes, and partner must sign the Male Consent Form.

2. Complete medical history and counseling of the couple

Pre-conception counseling

Female and partner must complete a Genetic Risk Factors questionnaire and RMN Medical History questionnaire

3. Complete Questionnaires.

- Female: Female Sexual Function Index (FSFI), SF-12, PHQ-9, FertiQoL, Epworth Sleepiness, Stop-Bang (Sleep apnea), Female Sexual Distress Scale (FSDS), Automated Self-Administered 24-hour Recall (ASA24), and Diet History Questionnaire (DHQ II)
- Male Partner: SF-12, PHQ-9, FertiQoL, Epworth Sleepiness, Stop-Bang (Sleep apnea), International Index of Erectile Function (IIEF), ASA24, and Diet History Questionnaire (DHQ II), Sun Exposure and Behaviour Inventory (SEBI), qADAM Questionnaire, and Psychosexual Daily Questionnaire (PDQ)

4. Physical Exams of Male and Female Subject

○ Female

- Vital signs, height, weight, hip and abdominal circumference, BMI
- Pap smear if necessary per current ACOG time-frame guidelines
- Standard pelvic and breast exam conducted by physician (or within past 12 months)
- Ferriman-Gallwey hirsutism scoring, acne lesion count

○ Male Partner

- Vital signs, height, weight, hip and abdominal circumference, BMI

5. Perform radiological exams.

Transvaginal ultrasound measuring uterine and ovarian characteristics

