- Collect urine and blood sample for RMN Biologic Repository if consent is signed
- Collect saliva sample if consented

7. Distribute Testing and Study Supplies
 - a. Distribute salivary collection kit, if consented.

Randomization Visit:

Randomization visit can take place regardless of menstrual cycle day and as soon after screening visit as subject and couple meet inclusion/exclusion criteria. Subjects will be informed in person of their randomization assignment. This is to allow for in person counseling of the lifestyle modification and answer face to face any concerns about their treatment assignment. Subjects will undergo during this visit: extensive orientation to the goals of the lifestyle modification, dispensing of all supplies and medications, and review of tracking and self-reporting requirements.

1. Perform limited physical exam, including weight and vital signs.
2. Orient subject to study treatment group including activity recommendations and use of meal replacements and orlistat.
3. Dispense study supplies such as Aria Wifi scale and Fitbit Activity tracker.
4. Dispense weight loss medication (orlistat) and provide instructions for ordering meal replacements on Nutrisystem’s website to subjects randomized to the extensive lifestyle modification arm.
5. Dispense intercourse and menstrual diaries.
6. Prenatal vitamins with folic acid dispensed.
7. Collect central core blood specimen as well as urine and blood reserve sample for ancillary studies (to be stored on site) (with consent). This will include hormonal assays for sex steroids (E2, P4, Testosterone), other reproductive hormones (SHBG), adipokines (leptin, adiponectin) and other hormonal and metabolic parameters that are determined relevant to the study.

8. Collect blood for DNA for the pharmacogenomic studies (with consent) to be stored on site.
9. Collect all available biospecimens from subject and male partner for RMN Biologic Repository (with consent).
10. Collect saliva specimen (with consent).

Monthly Visit during Lifestyle Modification Phase (Phase 1) (N = 3)

1. Perform limited physical exam, including weight, waist circumference, and vital signs (respiratory rate, pulse, and blood pressure).
2. Perform urine pregnancy test.
3. Collect menstrual and intercourse diaries, dispense new for next month.
4. Collect remaining study medications and perform pill count.
5. Dispense study supplies and medications, Prenatal vitamin, if applicable, orlistat.

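### The baseline step week falls in screening under Section 6.1 but after open-label randomization under Section 6.1.1, and nothing says which governs

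*Combined protocol and SAP*

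**What the plan says.** Four places deal with when the tracker is given out or when baseline steps are measured.

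- Section 6.1, in its paragraph on step goals, says: "Subjects will be asked to use the Fitbit Physical Activity Monitor during the screening phase to establish a mean number of steps". The mean is taken across 7 days. It is the baseline, and it has a working role: "This baseline average of steps will be used as the starting point for increasing average steps a day by 500 steps a day per week", up to 10,000.
- Section 7.2, screening visit(s): where screening is split over two visits, sites would "dispense the FitBit activity monitor at the second visit for subjects with a high probability of randomization".
- Section 6.1.1, which by its heading sets the baseline, says: "Subjects will be dispensed a Fitbit Physical Activity monitor during the randomization visit which will be used to determine average daily steps". The measurement lasts one week.
- Section 7.2, randomization visit, item 3: "Dispense study supplies such as Aria Wifi scale and Fitbit Activity tracker". Item 2 on the same list is orientation to the assigned group, including the activity recommendations.

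Two further statements fix what the woman knows at that visit. Section 4.1.1 says "The lifestyle modifications will be open label with adequate allocation concealment", and Section 5.7 says "Subjects will be immediately informed of their treatment assignment and orientation will begin". On the step program in the standard arm, Section 6.1.1 states: "This will be identical to the physical activity described above for the intensive physical activity group".

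**The concern.** Sections 6.1 and 6.1.1 place the baseline week on opposite sides of randomization. A site can follow either and believe it is compliant. Baselines from the two kinds of site would then measure different things: usual activity in one case, and activity in the first week after orientation in the other.

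The baseline is in operational use. It sets the first step target, and every later target is built on it. Sections 9.1.1 and 9.1.2 then monitor activity against those targets: women who miss their activity goals are contacted weekly, and first-month tracker data are reviewed for increases beyond the 500-step guideline. A displaced baseline changes who is flagged in either direction.

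A site following 6.1.1 as written would also hold no measure of activity from before assignment. That cannot be recovered later. Section 10.2 intends both groups to be encouraged and monitored toward the same amount of activity, and several tertiary aims in Section 2.3 (1, 2, 3, 6 and 12) concern physical activity. A pre-assignment value would be wanted for checking the first and for any use of baseline activity in the second.

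**Working it through.** No figure in the plan is in dispute, so the check is mainly a comparison of text.

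| Place | What it fixes | Timing relative to disclosure of arm |
|---|---|---|
| 6.1 | Dispensing implied; 7-day mean is the baseline | Before |
| 7.2, screening | Dispensing only, at a second screening visit | Before |
| 6.1.1 | Dispensing, and the week used for baseline | After |
| 7.2, randomization list | Dispensing only, listed after orientation | After |
| Table 7 | Row for dispensing tracker and scale | No mark seen in the screening column, but the columns are damaged in the text available; not relied on |

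**Step 1: can the two versions be read together?** One reading is that the tracker is given out in screening and merely explained again at randomization. Section 6.1.1 rules this out, because it uses the device dispensed at the randomization visit to obtain the week of average steps.

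**Step 2: does another rule force a pre-randomization week?** None was found. Section 7.2 expects that screening may be completed in one visit, in which case the second visit at which the tracker would be dispensed does not exist. The same section lets randomization happen as soon after screening as the couple meet the eligibility criteria. The inclusion criteria in Section 5.1 do not require a completed week of wear. A woman can therefore be randomized with no step data without any of these rules being broken.

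**Step 3: what would a shift in the baseline do?** The documents give no figure for how much orientation changes first-week steps, or in which direction, so the shift below is an assumption. An upward shift is shown.

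Weeks to reach the ceiling = (10,000 − recorded baseline) / 500.

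For an assumed usual level of 5,000 steps a day:

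- no shift: (10,000 − 5,000)/500 = 10 weeks
- +500: (10,000 − 5,500)/500 = 9 weeks
- +1,000: (10,000 − 6,000)/500 = 8 weeks
- +2,000: (10,000 − 7,000)/500 = 6 weeks

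For other assumed usual levels, under the same shifts of 0, 500, 1,000 and 2,000:

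- 3,000: 14, 13, 12 and 10 weeks
- 7,000: 6, 5, 4 and 2 weeks

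Each 500 steps of shift moves the schedule by one weekly increment until the ceiling is reached. A downward shift would lengthen the schedule at the same rate. These lines show how the rule responds; they do not estimate what would happen in this trial.

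**Step 4: does the primary analysis depend on this?** Section 10.4.1 powers the trial for 0.25 against 0.40 at two-sided 0.05. Recalculation gives 152 per arm (power 0.800), and 152/0.80 = 190 after 20% dropout. Both match Table 11, and step counts enter neither. The primary model in Section 10.9 adjusts for site and baseline BMI only.

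**The case against.** A reader might infer that knowledge of the arm contaminates the baseline differently in the two groups and so biases the comparison between them. The documents do not support that. Both arms have the same step program, the same 10,000 ceiling and the same monitoring of overshoot, so a response to step orientation would largely be common to both. The one arm-specific route is that the intensive arm starts diet and orlistat at about that time. Section 6.1, however, has meal replacements ordered and shipped after the visit, and nothing in the documents links either component to first-week steps.

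A reader might also infer that change from baseline in activity is biased. The plan specifies no such analysis. Steps are absent from the primary and secondary outcome lists, Section 10.9 names no step model, and the tertiary aims speak of physical activity or its amount, not of change. Aim 1, on the amount of activity during lifestyle modification, can be studied without a baseline.

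Third, Section 7.2 is not evidence for one side only. Its screening text and its randomization list point in opposite directions, and both deal with dispensing, not with measuring the baseline. Last, Section 6.2 refers further handling details to a Manual of Operations and Procedures, which is not part of these documents and may settle the question for sites.

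All of this limits the consequences. It does not remove the contradiction between 6.1 and 6.1.1, and the protocol should not depend on a manual to overrule one of its own sections.

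**Conclusion.** The contradiction stands. Section 6.1 puts the baseline week in screening, Section 6.1.1 puts it after randomization, Section 7.2 dispenses the tracker at both points, and no statement in the documents gives one precedence. It is more than a slip of wording, because the baseline starts every woman's step schedule and anchors activity monitoring. Under 6.1.1 it is a post-randomization measurement taken once the arm is known.

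The size of any shift is unknown, and the week counts above rest entirely on assumed shifts and assumed usual levels. A difference between arms is possible but not shown. The consequences are confined to step goals, adherence monitoring and any tertiary analysis that uses baseline activity. The primary outcome analysis and the sample size are not affected. The protocol should be corrected on this point.

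**What to change.** Reconcile Sections 6.1, 6.1.1 and 7.2 (screening text and randomization-visit list) and Table 7 to a single 7-day baseline week, completed before the arm is disclosed, which is the screening-phase timing that 6.1 already gives. Three things have to change together for this to work:

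- State when the tracker is dispensed to a woman whose screening is done in one visit.
- Amend the Section 7.2 sentence that allows randomization as soon as eligibility is met, so that it also requires the completed baseline week.
- State that any tertiary analysis using baseline activity uses this pre-randomization mean.

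This concerns the timing of a measurement only. It leaves the step increments, the ceiling and the monitoring rules as they are.

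The cost is protocol wording, some trackers issued to women who then fail screening, and about 7 days of wear before randomization. Section 7.2 already limits the second cost by reserving early dispensing for women likely to be randomized.
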